has been accrued in the craniofacial region. Indications include post-traumatic reconstruction, congenital deformities, post-surgical deformities (e.g. cancer resection), facial atrophy associated with HIV treatment, acne scars, and cosmetic correction of facial aging (2-25). Adipose tissue is injected into the subcutaneous planes and into deep fat pads. Volumes of adipose tissue injection in the facial region tend to range from several ml to over 100 ml. Procedures are often performed in a single stage, but staged fat injections are not uncommon. Advantages of autologous fat grafting for craniofacial reconstruction Autologous fat grafting has many advantages for craniofacial reconstruction compared with alternative treatments. Other standard methods of restoring soft tissue volume involve the surgical transfer of tissue flaps, either on a vascular pedicle or by microvascular technique. These flap procedures are much more invasive, carry a risk of donor site morbidity, and do not allow for precise. We have had significant and successful improvement in all subjects, with retention of volume in the range of 65%. Our basic science team recently published a paper in Plastic and Reconstructive Surgery Journal demonstrating in an animal model that a manual processing technique for separating the aqueous layer from the fat graft material without centrifugation provides superior volume retention after healing. This manual separation method requires less equipment in the operating room, making it more applicable for a variety of clinical settings in the military health system. Craniofacial Injuries Have Serious Psychosocial Sequele and Affect Quality of Life Many individuals who suffer significant facial disfigurement from injury experience psychological distress and impairment in functioning not limited to the acute phase of injury but over a longer term period of treatment, recovery and adjustment (26, 27). Symptoms of anxiety and depression and post-traumatic stress disorder are common—both before and after surgery (28, 29). In their study of individuals with severe facial lacerations and disfigurement, Levine and colleagues (30) noted the “powerful [influence] of facial appearance and body image on the quality of life” of these individuals. Clinical studies of facial trauma victims, using structured interview and self-report instruments, also document the common experience of social anxiety and social withdrawal—problems that can significantly compromise social and occupational functioning and engagement in social and leisure time activities—ultimately impacting the overall quality of life (31, 32). Facial burn victims report that interactions with strangers and with children and adolescents can be particularly discomfiting in response to visible non-verbal communications of negative affect (e.g. surprise, disgust) (27). Results of outcome studies of burn patients suggest that personal adjustment and quality of life are better predicted by psychosocial factors than site of injury (33). Pre- and post-surgical psychosocial factors such as social support, coping skills, and satisfaction with surgical outcomes are significant predictors of personal and social adjustment and quality of life outcomes, in addition to the physical outcomes of surgical intervention for disfigurement (34-36). Significant is the fact that there are few studies of the psychosocial impact of complex CMF battle injuries and post-surgical changes in psychosocial well-being and quality of life.

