2.2.1 **Does this research study involve an evaluation of the safety and/or effectiveness of one or more devices not currently approved by the FDA for general marketing?***

If YES, describe your **plan to prevent unauthorized use of the investigational device:**

2.2.1.1 **List each of the unapproved devices being evaluated in this research study. Specify for each listed device the corresponding Investigational Device Exemption (IDE) number or provide a justification for why you feel that this device and its use, as proposed in this research study constitute a non-significant risk (i.e., to include potential failure of the device) to the research subjects:**

Unapproved device

IDE #

Non-significant risk justification

There are no items to display

Section 2 - Research Design and Methods

- 2.3 **Summarize the general classification (e.g., descriptive, experimental) and methodological design (e.g., observational, cross-sectional, longitudinal, randomized, open-label single-blind, double-blind, placebo-controlled, active treatment controlled, parallel arm, cross-over arm) of the proposed research study, as applicable.**

This is an experimental intervention study with an observational component assessing clinical outcomes following the fat graft reconstructive surgery procedure using a manual separation process of the fat grafting material.

- 2.3.1 **Does this research study involve a placebo-controlled arm?**

* No

View: 2.04

Section 2 - Research Design and Methods

- 2.4 **Will any research subjects be withdrawn from known effective therapy for the purpose of participating in this research study?**

* No

- 2.4.1 **Provide a justification for discontinuing subjects from known effective therapy for the purpose of study participation.**

- 2.4.2 **Describe the risks to subjects associated with discontinuing them from known effective therapy for the purpose of study participation.**

View: 2.05

Section 2 - Research Design and Methods

- 2.5 **Will screening procedures (i.e., procedures to determine research subject eligibility) be performed specifically for the purpose of this research study?**

* Yes

- 2.5.1 **List the **screening** procedures that will be performed for the purpose of this research study. Do NOT include the inclusion/exclusion criteria in this section as they will be addressed in section 3; questions 3.13 and 3.14.**

Obtain Informed Consent, assignment of subject unique identifier

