3-Dimensional image The investigator or study staff will take photographs of the entire face (only) with the Canfield 3D camera system. The camera takes 2 simultaneous photographs of the face from different angles and makes a 3-dimensional image. The 3D camera system is not a medical device and is not regulated by the FDA. The pictures will be taken at the UPMC Aesthetic Plastic Surgery Center in a private room and will take approximately 10 minutes. Limited medical history and physical exam with a craniofacial exam by the investigator. The investigator will rate the appearance/volume of the graft site using a craniofacial volume and appearance grading scale.

2D Photographs the pictures will be taken at the UPMC Aesthetic Plastic Surgery Center in a private room and will take approximately 10 minutes. 2D photographs will be taken by the PI, Co-Investigator on the study or a research coordinator.

Digital Recordings: for subjects who consent, digital recordings (photography or video) will be collected at any and all portions of the subject's pre-operative, operative and post-operative study participation. These may include but not be limited to, videos of personal interviews, functional assessment testing and study physical exams or photos of the subject's follow-up course, biopsies, etc. We will ask the subject's permission to allow [name] and research team to use any and all these digital recordings for medical education and training, publication and media reports-and, in any mode of transmission, including but not limited to: print, email, television, internet, etc.

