Post graft study visits: POST op study visit (Day 3-6) This study visit will occur with the study investigator or research team and will take place approximately in 3-6 days post surgical procedure for the purpose of incision assessment and suture removal. The entire visit will take approximately 30-45 mins and will be scheduled with the subject prior to hospital discharge post fat graft procedure. 1.) Limited medical history and physical exam with craniofacial exam 2.) Collection of any Adverse events (Should an adverse medical event occurred prior to the visit and be reported by the subject, the research team will do due diligence to collect information pertaining to the event through subject report and /or medical record review and /or referring physician report) 3.) Collection of current medications, allergies and vital signs. Study visits (V1-V3): This study visit will occur with the study investigator or research team and will take place 7-21 days (+2 weeks) after the fat grafting surgical procedure, the entire visit will take approximately 2-3 hours. This visit will be scheduled by the research coordinator and discussed with the subject prior to the fat graft procedure. These research procedures will be repeated at both 3 months after the fat grafting procedure [Visit 2 (V2)] and at 9 months after the fat grafting procedure [Visit 3 (V3)]. The following research procedures will be completed: 1.) Subject weight and BMI measurement calculation 2.) 3-Dimensional photographs 3.) Limited medical history review and physical exam with a craniofacial exam completed by the PI and /or the Co-investigator 4.) 2D Photographs 5.) Psychosocial questionnaires assessment 6.) Collection of subject's vital signs (Temperature, heart rate (HR), respiratory rate, blood pressure (BP), medication profile to include prescription and vitamins / supplements, and allergies. 7.) The investigator will rate the appearance/volume of the graft site using a craniofacial volume and appearance grading scale 8.) A urine pregnancy test will be given to women of child bearing age prior to the CT scan. 9.) CT Scan with 3D renderings 10.) Structured Clinical Interview for DSM-IV (SCID) (Visit 3 V3 only) A Structured Clinical Interview for DSM-IV (SCID) will be included to evaluate the presence/absence of psychiatric disorders. This evaluation will be completed using a standard psychiatric diagnostic interview that enables determination of DSM-IV-based diagnoses. The information contained in the SCID will be collected by a research technician, a member of [name] clinical team who is experienced in psychosocial interviewing with patients. This SCID will take approximately 45-60 minutes of the subject's time to complete. 11.) Adverse Event Reporting (Should an adverse medical event occurred prior to the visit and be reported by the subject, the research team will do due diligence to collect information pertaining to the event through subject report and /or medical record review and /or referring physician report) Due to the subjects traveling distances who are enrolled into this trial, we have included a (+/-) of 14 days (2 weeks) for the completion of Visit 2 and Visit 3 as a convenience for the coordination of schedules.

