- 3.12 **Provide a statistical justification for the total number of subjects to be enrolled into this research study at the multicenter sites or this site.*** Described below: Serial computed tomography imaging will be performed to assess the total soft tissue volume before fat grafting and afterwards at three time points: immediately post-grafting, three months post-graft and nine month post-graft. Comparisons of the post-graft tissue volume to pre-treatment volume will be performed using a paired t-test model. Repeated measures analysis of variance will be used to evaluate change over time in all outcome measures. Using standard conventions of $\alpha=0.05$ and $\beta=0.8$, an enrollment of ten patients will provide sufficient power to detect a clinically meaningful differences in the volume of soft tissue between groups.. Based on published effect sizes for clinically significant medical outcomes on the SF-36 (i.e., 0.5 to 0.7), e.g., following surgery for dentofacial deformities ($d = 0.6$) (64), and medium (0.5 – 0.79) to large (0.8 to > 3.0) effect sizes on SF-36 social functioning outcomes of neck surgery (65) and orthopedic surgery (66), it is expected that a sample of 10 patients will provide sufficient power to detect a medium effect size ($d = 0.5$) on SF-36 measures of social functioning and quality of life, applying standard conventions of $\alpha = 0.05$ and $\beta = 0.8$. Outcome of facial appearance and soft tissue volume in subjects in this protocol will be compared to those subjects in PRO09060101. Significance level (adjusted for sidedness) = .025, standard deviation = 15 (15%), number of patients = 10, power= .0.8, difference in means = undefined, location of mean in one group as a percentile of the other group = undefined. The variable calculated was the minimum detectable difference. The probability is 80 percent that the study will detect a treatment difference at a two-sided 0.05 significance level, if the true difference between the treatments is 19.881 units or 19.8%. This is based on the assumption that the standard deviation of the response variable is 15 units or a 15% inter-individual coefficient of variation.

View: 3.13 - 3.15(a)

Section 3.0 - Human Subjects

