***Investigator** means the PI, co-investigators, and any other member of the study team, regardless of title, who participates in the design, conduct, or reporting of this research, as well as his/her spouse, registered domestic partner, dependents, or other members of his/her household. **The PI is responsible for ensuring that s/he and all other relevant members of the study team review the above questions describing Significant Financial Interests.**

**through the provision of funds, drugs, devices, or other support for this research

****Such as serving on the Board of Directors or Board of Managers or a position that carries a fiduciary responsibility to the company (e.g., CEO, CFO, CTO, or CMO).

7.3.1 **Provide the name of the investigator(s) and describe the nature of the Significant Financial Interest(s):**[name] conflict of interest involves the receipt of royalties and consulting fees for the Coleman cannules.

7.3.2 If you selected **A, B, C, or E**, please complete a [Standard Conflict of Interest Management Plan](#) and submit it with your protocol. Please provide all of the requested information, including the correct protocol number and title. **Incomplete, inaccurate, or unsigned forms will have to be edited and replaced.**

For all other financial interests (**D or F**), the COI Office will work with you to develop an appropriate COI Management Plan.

7.3.2 If you selected **B, D, E, or H**, please complete a [Standard Conflict of Interest Management Plan](#) and submit it with your protocol. Please provide all of the requested information, including the correct protocol number and title. **Incomplete, inaccurate, or unsigned forms will have to be edited and replaced.**

For all other financial interests (**A, C, F, or G**), the COI Office will work with you to develop an appropriate COI Management Plan.

*

View: Other Attachments

Supporting Documentation Section

References and Other Attachments

Additional documents:

Name	Modified Date	Version
References	4/25/2014 9:36 AM	0.01

View: Clinical Trials Registration

ClinicalTrials.gov is a registry and results database of publicly and privately supported clinical studies of human participants conducted around the world.

"[Applicable clinical trials](#)" are required by [federal law](#) to be registered in [ClinicalTrials.gov](#).

Applicable Clinical Trials (ACTs) are studies that meet the following criteria:

- The study is an interventional study AND

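### The only investigator rating of appearance is a live grade with no masking described; the analysed appearance score should come from a masked read of the photographs already taken

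*Combined protocol and SAP*

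**What the plan says.** - **Rating.** Section 2.6 places an investigator grade of the graft site at the pre-graft visit: "The investigator will rate the appearance/volume of the graft site using a craniofacial volume and appearance grading scale". Section 2.7 repeats it among the Visit 1 procedures: "7.) The investigator will rate the appearance/volume of the graft site using a craniofacial volume and appearance grading scale". Those procedures recur at Visit 2 (3 months) and Visit 3 (9 months). The grade is not listed at screening or at the day 3-6 post-operative visit.
- **Design.** Section 2.3, whose prompt invites a statement on blinding, answers: "This is an experimental intervention study with an observational component assessing clinical outcomes following the fat graft reconstructive surgery procedure". It names no masked assessor, and neither does any other section.
- **Role of appearance.** Section 1.1 makes change in facial appearance the overall objective. Section 1.2 includes it in Aim 1 and makes it part of the technique comparison in Aim 4. Section 3.12 states: "Outcome of facial appearance and soft tissue volume in subjects in this protocol will be compared to those subjects in PRO09060101".
- **Photographs.** 2D and 3D images are taken at the pre-graft visit (2.6) and at Visits 1 to 3 (2.7, for example "2.) 3-Dimensional photographs"). They carry only the subject ID (5.1.1). Section 2.17 lists their analysis first among the main outcomes, but no section says who scores them, on what scale, or whether that person is masked.
- **Other measures.** Volume is also measured on CT, with images reviewed by a head and neck radiologist (2.6). Satisfaction with appearance and quality of life are self-reported.

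**The concern.** A grade of appearance is a judgement. The person making it in clinic knows whether the visit is before or after grafting and how long after. With one treated group, that person also knows the processing technique. The team has a stated expectation: section 1.2 hypothesises good restoration of volume with most of the fat retained, and section 1.3 reports the group's own animal work in which processing "without centrifugation provides superior volume retention after healing".

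There is no concurrent control group in which the same expectation would operate and cancel out. Any rater shift is added to the true change, and no later analysis can separate the two. At stake are the size of the reported improvement on the graded scale, the reported course from Visit 1 to Visit 3 on that scale, and any contrast with PRO09060101 that uses it.

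**Working it through.** **1. What the text supports about masking.** No passage says that the rater is unmasked. It follows from two facts: no masking is described, and a live examination in a one-technique study cannot conceal the visit or the technique.

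**2. The plan's own figure.** Sections 2.18 and 3.12 give a minimum detectable technique difference of 19.881 units (SD 15, n = 10, power 0.8, two-sided 0.05). Taking 10 per group with 18 degrees of freedom:

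15 × √(2/10) × (t₀.₉₇₅,₁₈ + t₀.₈₀,₁₈) = 6.708 × (2.101 + 0.862) = 19.88.

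The noncentral t solution is 19.874. The figure therefore reproduces as 10 versus 10 independent patients. It assumes an unbiased response. A masked read changes none of its inputs.

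**3. Illustration of a rater shift, before versus after.** The documents give no bias size, so a range is assumed. Let δ be the mean shift in SDs of the paired change, with no true change and n = 10. The paired statistic is then noncentral t with 9 degrees of freedom and noncentrality δ√10, and the two-sided 5% critical value is 2.262.

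| δ | δ√10 | Chance of rejection |
|---|---|---|
| 0 | 0 | 5% |
| 0.25 | 0.791 | 10.9% |
| 0.5 | 1.581 | 29.3% |

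**4. Dependence on the unit.** If the 0.25 to 0.5 shift is in SDs of the score at a single visit, it must be divided by √(2(1 − r)), where r is the correlation between the two visits. The documents give no r.

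| r | δ in SDs of change | Chance of rejection |
|---|---|---|
| 0.2 | 0.198 to 0.395 | 9% to 20% |
| 0.5 | 0.25 to 0.5 | 11% to 29% |
| 0.8 | 0.395 to 0.791 | 20% to 61% |

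**5. The same illustration for a technique contrast.** Assume 10 per group, both graded on this scale, with the shift in SDs of the score. The noncentrality is δ√5 with 18 degrees of freedom, and rejection is 8.3% at 0.25 and 18.5% at 0.5. The documents do not say that PRO09060101 used this scale.

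**6. Size of the remedy.** 10 patients × 4 visits (pre-graft and Visits 1, 2 and 3) = 40 image sets.

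**The case against.** The strongest reply is that the graded scale may carry no conclusion. It is absent from the main outcomes in 2.17 and from the analysis text in 2.18 and 3.12, and Aim 1 names CT and photography as its tools. That stands, and it limits the point. A reader might infer that the live grade is the Aim 1 endpoint, but no section says so. What remains is that the live grade is the only investigator appearance rating described, while the photographs that could replace it have no stated reader, scale or masking.

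Other stronger readings are also unsupported:

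- **That all improvement, or any technique difference, is suspect.** CT volumetry and the self-reported measures are not graded by the investigator. Masking of the CT reader is also unstated, but that is a separate matter.
- **That a financial interest biases the comparison.** Section 7.3.1 discloses that one team member's "conflict of interest involves the receipt of royalties and consulting fees" for the cannulas. These deliver the fat, whereas the comparison concerns how the fat is processed. Nothing shows that the interest favours either technique or that its holder is a rater.
- **That 11% to 29% is this trial's error rate.** It rests on an assumed shift. The paired t-test is specified for tissue volume, and other outcomes receive repeated-measures analysis of variance. No change at all is also an unlikely null after up to 150 cc is injected into a volume defect. Distortion of the estimated size and course of improvement is the more realistic harm.

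It is also fair to object that masking will be incomplete: a visible defect can mark a pre-graft image, and swelling can mark Visit 1. Visits 2 and 3 should be easier to conceal, as should the cohort if comparable images exist.

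**Conclusion.** The point holds for the investigator-graded appearance scale. The grade is given live at the pre-graft visit and Visits 1 to 3, with no masking described, in a single-arm study whose objective is facial appearance. Change over time on that scale, and any technique difference on it, could reflect rater expectation. The conclusion does not extend to CT volume or to patient-reported outcomes.

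Its size cannot be derived from the documents. The 11% to 29% is an illustration that rests on three assumptions: a shift of 0.25 to 0.5 SD of the paired change, no true change, and n = 10. For the technique comparison, the documents record neither that PRO09060101 holds comparable photographs nor that it used the same scale. This is an inexpensive improvement worth making. It alters no stated sample size, significance level or power.

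**What to change.** In sections 2.6 and 2.7, state that:

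- the appearance score to be analysed is assigned from the existing 2D and 3D images after the last visit, on the same grading scale;
- images carry a reading code instead of the subject ID, are shown in random order, and hide the visit;
- the reader is an existing study-team member, preferably one who neither operated on nor examined that patient;
- the live grade is kept and reported as descriptive.

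Name this score in 2.17 as the measure of facial appearance. Fix the set of views sent to the reader, because 2.5.1 leaves the 2D views optional.

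For Aim 4, confirm whether comparable PRO09060101 images exist. If they do, mix them into the same read with the cohort hidden. If they do not, label the appearance comparison descriptive.

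The cost is image coding and the reading of about 40 sets, estimated at a few hours, plus any PRO09060101 sets. There is no new visit, procedure or hired reader. The remaining weakness is partial unmasking where the defect or early swelling reveals timing, and the report should say so.
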